10.4.3 Body Instrumentation

At Visit 1, body measurements (height, weight) will be performed.

10.4.4 Physical

The investigator will comprehensively evaluate the subject's appearance, skin, head/neck, heart, abdomen, urinary/reproductive system, limbs, musculoskeletal system, nervous system, lymph nodes, and other items at each visit. Clinically significant abnormal results observed before the application of the investigational device will be recorded in the medical history, and clinically significant abnormal results observed after the application of the investigational device will be recorded as adverse events.

10.4.5 Laboratory tests

The investigator will investigate the following items from the subject's blood and urine at Visit 1, Visit 2, and Visit 4, and if necessary, this test may also be performed at the un-scheduled visit at the investigator's discretion. If the results are already available within 4 weeks prior to Visit 1, the results can be replaced with a screening test. Subjects who do not meet the screening test results for Inclusion/exclusion may be re-tested only once, in which case the re-test results will be used. If the V2 visit date is within 7 days of the V1 visit date, the V1 laboratory test results can be substituted for the V2 laboratory results. In the case of pregnancy response testing, urine hCG pregnancy test (if not allowed, serum test is replaced) may be performed only for women of childbearing potential and may be performed at each visit point if necessary at the discretion of the investigator.

Hematological tests	white blood cell (WBC), WBC with differential (Lymphocyte, Monocyte, Eosinophil, Basophil, NeutrophilSegment), red blood cell (RBC), hemoglobin (Hb), hematocrit (Hct), platelet count (PLT)
Hematological Chemical Tests	alkaline phosphatase (ALP), aspartate aminotransferase (AST), alanine transaminase (ALT), Gamma Glutamyl Transpeptidase (GGT), total bilirubin, albumin, serum creatinine, blood urea nitrogen (BUN)
Urinalysis	Specific Gravity, Color, pH, Protein, Glucose, Bilirubin, Blood, WBC, Urine hCG pregnancy test (This test will be performed only for women of childbearing age before menopause, only at the screening visit (Visit 1), and if necessary, additionally performed at the last visit (Visit 4).)

Laboratory test results are classified as normal and abnormal (NCS, CS), and if laboratory test results after application of the investigational device are judged to be clinically significant compared to before application, they are reported as adverse events and findings on abnormal values are recorded.

10.4.6 Vital signs

The investigator will measure the subject's seated systolic/diastolic blood pressure, pulse, and body temperature at each visit to investigate vital signs. All vital signs will be examined with the subject resting for at least 5 minutes. Clinically significant abnormal results observed before the application of the investigational device will be recorded in the medical history, and clinically significant abnormal results observed after the application of the investigational device will be recorded as adverse events.

10.4.7 Evaluation of Inclusion/Exclusion Criteria and Assignment of Randomization Numbers

Based on the observations and examination items at Visit 1 and Visit 2, the Inclusion/exclusion criteria for suitability to participate in this clinical trial will be confirmed. Only subjects who are finally confirmed at Visit 2 will be assigned a registration number according to '9.3 Subject Assignment'.

10.4.8 Surgery

The surgery specified in Visit 2 will be performed.

[figure not shown]
10.4.9 Investigational device Application

After surgery, the test device CollabARRIER® or the control device Guardix-sol will be applied to the application area and the application amount will be collected.

10.4.10 MRI Scar score

At 6 weeks after the application of the investigational device, the subject will present to the institution for MRI scans of the surgical site. The MRIs taken will be classified by subject, and when evaluated by an independent evaluator, the subject information from all photographs of the institution will be blinded to ensure that the blinding is maintained. The same imaging will be performed at all institutions by referring to the following information and pictures [16, 17].

- A. Axial slice thickness: The slice thickness is taken at a distance of 3 ~ 4 mm from the sagittal plane centered on the intervertebral disc at the surgical site.
- B. In an axial arrangement, each cross-section for the axial plane contiguous to the axial plane in five axes close to the center of the intervertebral disc is quadrant perpendicular to the thecal sac.
- C. T1-weighted Gadolinium will be taken both non-enhanced before administration and enhanced images after administration.

This clinical trial is a multicenter clinical trial, and although the instruments used by each institution are different, the sequence is uniformly shot and the same is recorded, and the parameters of each device are adjusted to achieve the same image as allowed. The location recording of supradural fibrosis on MRI and the evaluation of adhesions will be made by an independent evaluator, and the degree of scar will be scored for 20 cross-sections with 5 MR images in 4 quadrants per subject. The largest score among the total 20 SCA scores evaluated will be selected to compare and evaluate the mean value of the scar score between the test group and the control group, and the score according to the degree of scar of the dura mater will be evaluated as 0 ~ 4 points, and the relevant details are shown in the table below.

score	Details
0	No / trace scar
1	> 0% and ≤ 25% of quadrant filled with scar
2	> 25% and ≤ 50% of quadrant filled with scar
3	> 50% and ≤ 75% of quadrant filled with scar
4	> 75% of quadrant filled with scar

The investigator creates a folder for each subject and keeps the photo file. In the created folder, the photographs are stored in the form shown in the table below, separating the subject's visit time and the test group and control group. If the investigator saves each photo in the form of an electronic file on an external hard drive or USB, the monitoring personnel of the clinical trial site can create a material receipt sheet and send it to the independent data manager. Photographs should be sent at least once a quarter, and may not be sent if there are no registered patients. Photographs should be sent in a compressed folder if necessary, and the folder name should be the same. For details related to the evaluation procedure of independent evaluators, please refer to 'Attachment 7: Independent Evaluation Manual'.

Subject RX-NN photo folder name	Protocol No_Subject Number
Example Photo Folder Name of Subject R1-001	DRT-04_R1-001
Photographic name for subject identification	Protocol No_Subject Number_Visit Date_Placement Group
Example of test group photo name of V4 subject R1-001	DRT-04_R1-001_V4_Test Group

10.4.11 100 mm Visual Analogue Scale(VAS)

At the preoperative time point (baseline) and at 3 and 6 weeks after the application of the investigational device, subjects will come to the hospital for efficacy evaluation and undergo a 100 mm Visual Analogue Scale (VAS) Evaluation for back and leg pain. In the case of legs, VAS evaluation will be performed only on one of the two legs with severe pain. The 100 mm VAS marks the left end as no pain '0' and the right end as '100' for severe pain on a 100 mm parallel line. The subject draws a vertical line exactly on the parallel line and measures the mm from no pain (0) to the vertical line to

check the value. For details, refer to 'Annex 3. 100 mm Visual Analogue Scale (VAS) Evaluation Sheet'.

10.4.12 Oswestry Disability Index(ODI)

At the preoperative time point (baseline) and at 3 and 6 weeks after the application of the investigational device, subjects will come to the clinic for efficacy Evaluation and undergo an Oswestry Disability Index (ODI) Evaluation of the limitation of daily living. Subjects will be evaluated in 'Annex 4. The Oswestry Disability Index (ODI) questionnaire will be used to evaluate the 'Oswestry Disability Index (ODI)', and the scoring method of the questionnaire is as follows [19].

Oswestry Disability Index(ODI) Scoring Method	
The maximum score for each section within the questionnaire is '5 points', and the total score for all 9 sections combined is '45 points'. In each section, if you check phrase 1, the score for that question item is '0 points', and if you check the last phrase (phrase 6), the score is '5 points'. Once all 9 sections are completed, the score will be calculated as follows:	
Calculations:	
$[\text{Total score} / 5 \times \text{sections answered}] \times 100 = \underline{\hspace{2cm}} \%$	
Example (1): If all sections are checked and the total score is 16 $[16 (\text{Total Score}) / 5 \times 9] \times 100 = 35.6\%$	
Example (2): If one section is missing or not applied, and the total score is 16 $[16 (\text{Total Score}) / 5 \times 8] \times 100 = 40.0\%$	

10.4.13 Adverse Case Investigation

Adverse events that occur after the application of an investigational device will be identified, and the investigator will be trained to voluntarily report any adverse events that occur. In addition, the investigator will check whether adverse events occur through interviews and medical examinations during regular visits during the clinical trial.

The investigator will observe and record the adverse events that appear after the application of the investigational device by examining the subject on each visit day, and record in detail the time of symptom onset, termination, severity, progress, action, outcome, severity, and causality of the adverse event.

Laboratory tests will also be reviewed, and abnormal results will be assessed for clinical significance. Clinically significant laboratory test abnormalities will be followed up until they return to acceptable values or can no longer be followed up (loss of follow-up or withdrawal of informed consent). However, if the principal investigator determines that the adverse event does not require further follow-up, the clinical trial may be terminated at the end visit (Visit 4).

11. PREDICTED SIDE EFFECTS AND PRECAUTIONS FOR USE

11.1 Investigational Device

1. Warnings (contraindications)
 - 1) Do not use on patients with contamination or infection at the surgical site.
 - 2) Do not use in patients with hypersensitivity to porcine-derived products.
 - 3) If you experience an allergic reaction or infection during the use of this product, do not use it and seek appropriate treatment according to your doctor's instructions.
 - 4) This product should not be used when excessive exudate, bleeding, acute edema, or symptoms of infection are not controlled.
 - 5) This product is prohibited for use other than medical use or use.
 - 6) In case of unexpected local and systemic allergic reactions, you should consult a doctor.
2. Precautions for use considering the characteristics of medical devices
 - 1) It is not studied and is prohibited for the following patients:
 - ① Patients with coagulation diseases of lymphatic fluid or blood or patients who have received coagulants
 - ② Patients with immunosuppressed or autoimmune diseases
 - ③ Patients with severe hepatic or renal disease or who have undergone surgery involving opening of the gastrointestinal tract or urinary tract
 - 2) Patients who have received oral or parenteral hypoglycemic drugs for diabetes are not studied and are administered with caution.
 - 3) When this product is used in combination with other drugs such as anti-adhesion products and absorbent hemostatic agents, its safety and efficacy have not been confirmed in animal tests.
3. Adverse reactions (side effects) that may occur as a result of the use of medical devices
 - 1) The surgeon should inform the patient that the following symptoms may appear immediately after injection of this product or after a certain period of time, and report to the salesperson when these symptoms occur.
 - Infection, allergies, pain, inflammatory reactions, etc.
 - 2) If the above reactions persist or other side effects occur, consult a specialist immediately for treatment.
4. General Caution
 - 1) Depending on the storage method, it should be stored until use.
 - 2) Do not reuse for single use.
 - 3) Check sterile packaging and do not use products with torn or damaged packaging.
 - 4) Do not use products that have expired.
5. Use for pregnant, lactating, fertile women, newborns, infants, and children

1) Jaundice may occur, so it should not be used in late pregnancy, premature babies, primiparous babies, or newborns within the first month of life.

2) The safety of using foreign plants in pregnant, parturient or lactating women has not been established, so they should be used with caution and under the judgment of a doctor.

3) Since there has been no clinical application of this product to pregnant women, it is used when it is judged that there is a therapeutic benefit when applying this product to pregnant women.

6. Precautions for application

1) Do not administer by the IV, IM, and SC routes.

2) Do not re-sterilize.

3) Only products that have been sterilized must be used, and should not be used if the packaging has been opened.

4) This product is sterile, so once used, it is not reused.

5) Do not use sterile packaging that has been opened or damaged.

6) It should be used according to the usage method for safety.

7) If bleeding is severe, it is used after hemostatic treatment.

8) Check the product's usage period.

9) It is contraindicated for use in areas where safety and efficacy have not been clinically verified.

10) Do not use it in places where bacteria are infected, where the area to be treated is infected, or where the infection is in progress without a special prescription from a medical professional.

11) It is not used by anyone other than those who have received training or more than professional training or qualifications.

12) Do not mix with non-standard or unlicensed medical devices. If you experience allergic reactions or symptoms of infection while using the product, do not use it and receive appropriate treatment according to the instructions of a doctor or pharmacist.

7. When it is necessary to prevent safety accidents

1) When used outside the operating room or clean room, side effects such as fever and inflammatory reactions may occur due to infection caused by external contaminants, so it should be used under sterile conditions.

11.2 Control device

1. General Notes

1) This product is sterile, so make sure it remains sterile during the procedure and do not use it after the sterilization expiration date has passed.

2) Do not use the container if it shows signs of damage or moisture after checking the contents before use.

3) Before inserting this product into the surgical site, the surgeon should absorb and remove excess fluid from the injection site.

2. Precautions for handling

1) This product should be stored at room temperature before use.

- 2) This product is supplied sterile. Do not re-sterilize
- 3) This product is for one-time use and should not be reused.

3. Contraindications

- 1) Patients who are prohibited from receiving
 - ① This product should not be used on patients who are currently infected or contaminated with the surgical site.
 - ② Do not use this product in patients with hypersensitivity.
- 2) Careful dosing
 - ① This product has not been studied in patients with lymphatic fluid or blood clotting disorders or patients who have received coagulants.
 - ② This product has not been studied in patients who have received oral or parenteral hypoglycemic drugs for diabetes.
 - ③ This product has not been studied in immunosuppressed patients or patients with autoimmune diseases.
 - ④ This product has not been studied in patients with severe liver or kidney disease or in patients who have undergone surgery involving opening the gastrointestinal tract or urinary tract.
 - ⑤ When this product is used in combination with other drugs such as anti-adhesion products and absorbable hemostatic agents, its safety and efficacy have not been confirmed in animal tests.
 - ⑥ This product is not recommended for use during pregnancy. After using this product, it is recommended to avoid pregnancy until the end of the first menstrual cycle.

4. side effect

- 1) contagion
- 2) Allergic reactions
- 3) pain
- 4) Inflammatory response

12. CRITERIA FOR SUBJECT DISCONTINUATION OR DROPOUT

12.1 Discontinuation or Dropout of the Clinical Trial

If the following cases occur, all or part of the clinical trial sites will review the existence of the clinical trial based on the relevant clinical trial plan.

- 1) If the situation observed during the clinical trial is determined to be unreasonable for the clinical trial to continue, the principal investigator must request the clinical trial review board to stop the clinical trial, and may suspend the clinical trial according to the decision of the clinical trial review board.

- 2) If the subject is discontinued due to the occurrence of an adverse event/serious adverse event that makes it difficult to proceed with the clinical trial (if the investigator determines that the study should be stopped)
- 3) When a change in the clinical trial plan is required, but the site is unable to respond to it
- 4) When the head of the site gives an amendment order based on the opinion of the review committee of the site and the sponsor is unable to approve it,
- 5) If the director of the site orders the suspension of the clinical trial based on the opinion of the institution's review board that the clinical trial cannot be continued.
- 6) If the site has committed serious or continuous violations that are different from KGCP and this clinical trial agreement

In addition, if the sponsor decides to suspend or discontinue the clinical trial, he or she shall promptly notify the Clinical Trial Review Committee and the principal investigator in writing of the purpose and reason. However, if there is a separate notification regulation for suspension or suspension of clinical trials depending on the institution, it shall be followed.

If the principal investigator receives a notice from the sponsor regarding the suspension or suspension of the clinical trial, the principal investigator shall promptly notify the subject of the suspension or suspension of the clinical trial and ensure appropriate treatment and follow-up treatment.

12.2 Handling of Discontinuation

- 1) If the clinical trial is suspended, the principal investigator shall summarize and deliver the CRF of the subject to the time of suspension, the progress status and results of the clinical trial to the sponsor, and return all trial-related materials (CRF and investigational device, etc.) to the sponsor.
- 2) If the study is discontinued, the principal investigator shall notify the IRB in writing of the study suspension.

12.3 Subject dropouts

- 1) If the following are found during surgery
 - A. If there must be other devices left at the surgical site that may interfere with the interpretation of the study results
 - B. If dural rupture and dural hole are found during surgery
 - C. Epidural fat placement
 - D. If you have a herniated disc and need surgery on more than one level
 - E. If you are applying a sealant or making other attempts to repair a fibrous annulus tear
 - F. If a tumor in the spine is found during surgery
 - G. Entering the dura mater during surgery
 - H. If spinal fusion is required
 - I. If the hemostatic agent must remain at the surgical site
, but if it is cleaned after stopping the bleeding, it will not be dropped out.
 - J. If antibiotic powder is injected into the surgical site
(antibiotic cleaning is only allowed before the application of the medical device, not after applicati

on.)

K. When the following products are applied to exposed nerve elements

- Amniotic tissue or amniotic fluid
- adhesive
- steroid
- Platelet-rich plasma fluid
- Gel Foam
- Allograft tissue
- Fibrin Adhesive
- Dural patch

- 2) The subject (or legal representative) voluntarily wishes to discontinue the trial.
- 3) Surgery that may affect safety and efficacy evaluation, or when using other drugs and procedures in conjunction with other drugs and procedures
- 4) If an adverse event occurs during follow-up observation that makes it difficult to continue the clinical trial
- 5) Subjects who are not able to continue to follow up on the treatment of this clinical trial due to loss of contact during this clinical trial
- 6) Inclusion/exclusion criteria non-conformity confirmed since enrollment in the trial
- 7) If the principal investigator deems it inappropriate as a subject (if he does not comply with the investigator's instructions, if it is judged that he or she can no longer participate in the clinical trial in terms of safety or ethics due to a change in the subject's condition, etc.);

12.4 Handling of dropouts

- 1) If the subject drops out midway, the reason for dropout and the data related to the clinical trial that was conducted before the dropout will be recorded and kept.
- 2) If the subject fails to come to the hospital during the test, the subject's health and wellness should be checked and the reason should be clarified.
- 3) Those who drop out will be included in the statistical processing of safety and efficacy evaluation unless there is a valid reason or basis.
- 4) The data obtained through clinical trials should have a dataset for safety analysis and efficacy analysis, and if there is a defect in the data, the appropriate correction method should be presented in the research protocol, and the analysis should be performed after calibration.

13. CRITERIA, EVALUATION METHODS, AND INTERPRETATION METHODS FOR EFFICACY EVALUATION (STATISTICAL ANALYSIS METHODS)

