13.1 Definition of Analysis Group

The data obtained from the subjects through this clinical trial will be divided into the Safety Set, FA (Full Analysis) Set. Statistical analysis will be performed by dividing it into PP (Per Protocol) Sets. The main population of this trial will be the PP Set, the secondary evaluation group will be the FA Set, and the safety evaluation will be analyzed with the Safety Set.

Full Analysis Set (FA Set)

Subjects who have been applied to an investigational device at least once after randomization and who can obtain information about the results of the primary efficacy evaluation after baseline are eligible.

Per-Protocol Set (PP Set)

The PP Set is for subjects included in the FA Set who have completed the clinical trial according to the clinical trial protocol without any serious protocol violations, and subjects who fall under the following cases will be excluded from the PP Set.

- 1) Dropout
- 2) Violation of Inclusion/Exclusion Criteria
- 3) Taking prohibited drugs or using prohibited treatments (except for other purposes)
- 4) Other cases that may be considered serious violations of the plan

Safety Set

Subjects who have been applied to an investigational device at least once after randomization and whose safety-related data have been evaluated at least once will be included.

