14.2 Record of Adverse Events

From the time of application of the investigational device to the date of the last visit, undesirable and unintended symptoms (e.g., abnormalities in laboratory tests), symptoms, and diseases that occur in the subject will be recorded as adverse events. Symptoms, symptoms, or diseases that appeared before the application of the investigational device will only be considered as adverse events if they worsen after the application of the investigational device.

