17. MATTERS CONCERNING THE SUBJECT'S CARE AFTER THE TRIAL

Subjects who are dropped out of the clinical trial or have no response will be instructed to receive other appropriate treatments, and subjects who have been terminated from the clinical trial will be able to receive medical treatment at any time according to the doctor's advice in case of unexpected delayed adverse events. The compensation evaluation criteria for medical expenses, etc. incurred during medical treatment/treatment are 'Attachment 2. Regulations on Compensation for Victims'.

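### For subjects who received the device and then drop out, the plan provides no collection of new adverse events to week 6, yet they stay in the crude incidence denominator

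*Combined protocol and SAP*

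**What the plan says.** **Who is dropped.** Section 12.3 lists reasons that can arise once the device is in place: "Surgery that may affect safety and efficacy evaluation" or other drugs and procedures (item 3), an adverse event during follow-up (item 4), "Inclusion/exclusion criteria non-conformity confirmed since enrollment in the trial" (item 6), and investigator judgement, including non-compliance (item 7). Item 1 covers findings during surgery, some of which could follow application. Section 14.2.2(1) adds that a subject's trial is stopped after a serious adverse event.

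**What is kept and recorded.** Under 12.4(1), "the reason for dropout and the data related to the clinical trial that was conducted before the dropout will be recorded and kept". Under 14.2, adverse events are recorded "From the time of application of the investigational device to the date of the last visit". For a subject who fails to attend, 12.4(2) asks that "the subject's health and wellness should be checked and the reason should be clarified". Existing events are followed under 14.2.2(2), serious ones under 14.3.2, and significant laboratory abnormalities under 10.4.13. Section 17 offers subjects who have finished the trial medical care "in case of unexpected delayed adverse events".

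**How they are analysed.** Under 12.4(3), "Those who drop out will be included in the statistical processing of safety and efficacy evaluation unless there is a valid reason or basis". The Safety Set in 13.1 takes subjects who received a device and "whose safety-related data have been evaluated at least once". Section 13.6.1 reports subjects with events, incidence and event counts; 13.2 leaves missing values uncorrected.

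**The concern.** The device is applied once, before closure, and leaving the trial does not undo the exposure. A subject who drops out on day 10 is still at risk of infection, inflammation, allergy or pain, the reactions named in 11.1. The plan gives no route by which a first event on day 20 would reach the database.

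That subject still counts fully in the denominator. Visit 2 includes an adverse event check (10.3.2), so someone dropped on the day of surgery after application can qualify for the Safety Set. A person observed for days then weighs the same as one observed for six weeks, and any resulting error in incidence runs downward.

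Safety is part of the stated objective (4.1). Section 9.5.2 also says that the investigator knows the assigned device (although its second paragraph describes the investigator as blinded), and 12.3(7) lets a subject be dropped on judgement. Shortened observation therefore need not be equal between arms.

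**Working it through.** **1. Is there any provision for new events after dropout?**
- 12.4(1): addresses data from before the dropout.
- 14.2: ends at the last visit. For a completer this is Visit 4; for a dropout it could mean the last visit attended or the planned Visit 4.
- 12.4(2): a health check after a missed visit, with no instruction to record adverse events.
- 14.2.2(2), 14.3.2, 10.4.13: continued follow-up of events or abnormalities that already exist.
- 10.3.5: unscheduled visits, at the investigator's judgement.
- 17: care, not data collection.

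None of these schedules collection of new events to week 6.

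**2. Expected number of dropouts (7.4).** The plan's figure reproduces. With margin 0.57, SD 0.774, true difference 0 and one-sided alpha 0.025, a two-sample t-test with 30 per arm has power 0.80086. Inflation gives 30 / (1 − 0.10) = 33.3, rounded up to 34 per arm. Expected dropouts are 68 − 60 = 8, or 4 per arm.

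**3. Effect on crude incidence.** The documents give no adverse event rate and no dropout times, so both are assumptions. Let p be the six-week risk, f the fraction of six weeks observed before dropout, k = 4 and n = 34. With constant hazard, the risk up to dropout is p_d = 1 − (1 − p)^f, and crude incidence is c = [(n − k)p + k·p_d] / n.

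Worked case, p = 10% and dropout at day 14 of 42: p_d = 1 − 0.9^(1/3) = 3.45%. Then c = (30 × 0.10 + 4 × 0.0345) / 34 = 3.138 / 34 = 9.2%. The expected shortfall is 3.4 − 3.138 = 0.26 subjects per arm.

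| Assumed p | Dropout right after application (f = 0) | Halfway (f = 0.5) |
|---|---|---|
| 5% | 4.4% | 4.7% |
| 10% | 8.8% | 9.4% |
| 20% | 17.6% | 18.9% |
| 50% | 44.1% | 47.6% |

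The relative loss is 4/34 = 11.8% for f = 0, and 4.9% to 5.8% for f = 0.5.

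**4. If dropouts carry higher risk.** Suppose dropouts have r times the completers' risk and leave at once. Expected cases are 30p + 4rp, of which 30p are seen, so the relative loss is 4r / (30 + 4r). For r = 2 this is 8/38 = 21%; for r = 3 it is 12/42 = 29%.

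**5. Subjects dropped because of an adverse event.** Take 30 completers at 20% risk (6 expected cases) plus 4 subjects dropped for an event. Any-event incidence is (6 + 4) / 34 = 29.4%, with or without later follow-up. For these subjects, the possible loss is confined to event counts, other preferred terms, and later device effects or serious events.

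**6. Chance of seeing at least one event of 5% true risk in an arm.** All 34 followed: 1 − 0.95^34 = 82.5%. Four dropped at day 14: 1 − 0.95^(30 + 4/3) = 80.0%. Four contributing nothing: 1 − 0.95^30 = 78.5%.

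**The case against.** A reader might infer that safety collection ends at dropout. The documents do not say so. Section 12.4(1) states what is kept, without stating that nothing more is gathered, and 10.4.13 calls Visit 4 the end visit, so the window in 14.2 can be read as running to week 6. A dropout absent from Visit 3 or 4 might also fall under the health check in 12.4(2). This stands: the gap is one of silence, and it concerns new events only.

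A reader might also infer that subjects dropped for an adverse event or reoperation lower the overall event rate. For the former, step 5 shows that they do not lower any-event incidence. A reoperation that involves unplanned hospitalisation, or results from an adverse event requiring admission, meets the serious event definition in 14.1.3, is reported within 24 hours (14.3.1) and is followed. This also stands.

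A third tempting inference is that everyone dropped under 12.3(1) is exposed. Many of those findings precede application, and subjects without the device are outside the Safety Set.

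Finally, 12.4(3) allows dropouts to be left out for a valid reason, 13.6.1 plans no hypothesis test on adverse events, and differential loss by arm is a possibility for which the documents give no evidence. These points limit the consequence. They do not supply the missing collection: the exclusion clause has no criteria, and a descriptive incidence can still be too low.

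**Conclusion.** The point holds for new adverse events after dropout in subjects who received the device. Following the plan as written can miss them, and the crude denominator turns a missed event into an apparent non-event. It does not support a flat statement that incidence is understated: that requires a first event, or an additional event of another kind, after dropout and before week 6.

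Under equal constant risk with 4 of 34 dropouts per arm, the relative shortfall is about 5% to 12% for dropout between application and mid-follow-up. It reaches 21% to 29% if dropouts carry two to three times the risk and leave at once. These sizes rest on assumed risks and dropout times. They are also upper bounds on what a change could recover: the 10% allowance covers any loss of response data, and so can include withdrawn consent, lost contact and subjects who never received the device. The primary analysis is unaffected, because 13.1 excludes dropouts from the PP Set. The change is worth making because it improves safety ascertainment at little cost.

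**What to change.** In 12.4 and 14.2, separate leaving the efficacy evaluation from leaving safety follow-up:
- For every subject with a device applied, unless consent is withdrawn, continue the safety items already scheduled: adverse event check, physical examination and vital signs at Visits 3 and 4, and laboratory tests at Visit 4. Do the adverse event check by telephone if the subject does not attend.
- Define the end of adverse event recording as Visit 4, or the equivalent week-6 date for subjects who leave early.
- Reconcile this with 14.2.2(1), so that it is clear what stops for a subject after a serious adverse event and whether safety data collection continues.
- Flag data obtained after dropout so that they do not enter the PP Set.

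The protocol summary already reports 69 subjects enrolled. If follow-up is complete, report the duration of safety follow-up by arm and add exposure-adjusted adverse event summaries beside the crude incidences.

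The cost is protocol wording and a few additional contacts: at most about 8 subjects on the plan's own dropout allowance, and fewer once withdrawn consent and lost contact are set aside. No new type of assessment is needed.
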